4.2.3.1.1 Measurement of HCV RNA

HCV RNA levels in plasma will be measured on blood samples drawn from each subject at various time points prior to, during, and after dosing, as indicated in the Trial Flow Chart (Section 6.0). Samples are collected and processed as per instructions provided by the central laboratory manual (assay type indicated in central laboratory manual).

Results from the sample collected at the screening visit are used to determine eligibility. Samples collected at other time points are used for efficacy analyses. They are also used to identify subjects who meet virologic failure criteria.

The nomenclature detailed in [Table 9](#) will be used when describing HCV RNA levels:

Table 9 Nomenclature for Describing HCV RNA Levels

Abbreviation	Definition	HCV RNA Level
TND	Target not detected	HCV RNA not detected
TD(u)	Target detected but unquantifiable	HCV RNA < LLOQ
TD(q)	Target Detected, quantifiable	HCV RNA \geq LLOQ

4.2.3.1.1.1 Definition of Efficacy Endpoints

Efficacy will be defined at different time points during the trial. Specific endpoints are:

- SVR₁₂ (sustained virologic response 12 weeks after the end of all study therapy). The subject has HCV RNA < LLOQ (either TD[u] or TND) 12 weeks after the end of all study therapy.
- SVR₂₄ (sustained virologic response 24 weeks after the end of all study therapy). The subject has HCV RNA < LLOQ (either TD[u] or TND) 24 weeks after the end of all study therapy.

4.2.3.1.1.2 Definition of Virologic Failure: Non-Response, Rebound, Virologic Breakthrough and Relapse

Lack of efficacy at different time points in the trial will be categorized as:

- Non-response: Subject has HCV RNA detected at end of treatment without HCV RNA $<$ LLOQ on treatment (note that breakthrough is captured below).
- Rebound: Subject has a rebound defined as $>1 \log_{10}$ IU/mL increase in HCV RNA from nadir while on treatment and confirmed from a separate blood draw within 2 weeks.
- Virologic breakthrough: Subject has a confirmed HCV RNA \geq LLOQ (TD [q]) after being $<$ LLOQ previously while on treatment. Confirmation is defined as an HCV RNA \geq LLOQ from a separate blood draw repeated within 2 weeks.
- Relapse: Subject has a confirmed HCV RNA \geq LLOQ (TD [q]) following end of all study therapy, after becoming undetectable (TND) at end of treatment. Confirmation is defined as an HCV RNA \geq LLOQ from a separate blood draw repeated within 2 weeks.

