4.2.3.1.2 Viral Resistance Measurements

HCV resistance measurements

Resistance-associated variants (RAVs) of the hepatitis C virus can lead to increased risk of failure to DAA therapy. In addition, subjects with virologic failure may develop RAVs.

Blood samples for viral resistance assays are collected on all subjects at Baseline (Day 1) to determine the impact of baseline RAVs on response to EBR and GZR.

To better understand the presence of RAVs after treatment with a regimen containing EBR/GZR, samples will be collected at virologic failure confirmation visits and all follow-up visits after virologic failure is confirmed. Samples will be tested for any subject meeting virologic failure criterion who has detectable virus >1000 IU/mL. These same subjects who meet any virologic failure criterion will have samples collected at all subsequent follow-up visits to be assessed for RAVs, if the virus is detectable and >1000 IU/mL.

Subjects who fail due to early discontinuation of study medication and continue in the trial will also have samples collected and tested for RAVs at each follow-up visit, if the virus is detectable and >1000 IU/mL.

Analysis of RAVs will entail a variety of techniques that may include population sequencing and/or next generation sequencing. Additionally, genotypic and investigational assays may be employed to differentiate virologic failure from re-infection. Resistance testing may also be performed on leftover HCV RNA plasma samples.

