7.1.5.5 Follow-Up Visits

At the completion of study therapy subjects will return to the study site for follow-up visits at 4, 12, and 24 weeks after the last dose of study drug.

Subjects who discontinue because they have met criteria for virologic failure (Section 4.2.3.1.1.2) while on study therapy should complete an Early Discontinuation Visit as outlined in the Trial Flow Chart (Section 6.0), and return to the study site for follow-up visits at 4, 12, and 24 weeks following confirmation of virologic failure. Subjects who meet the virologic failure criterion for relapse (HCV RNA \geq LLOQ following the end of all study therapy, after becoming undetectable [TND] at the end of treatment) will return to the study site for the remainder of their follow-up visits (e.g., 4, 12, and 24 weeks) as outlined in the Trial Flow Chart (Section 6.0).

Subjects who discontinue for reasons other than virologic failure should complete an Early Discontinuation Visit as outlined in the Trial Flow Chart and return to the study site for follow-up visits at 4, 12, and 24 weeks following the discontinuation of treatment.

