8.5 Analysis Populations

8.5.1 Efficacy Analysis Population

The Full Analysis Set (FAS) population will serve as the primary population for the analysis of efficacy data in this study. The FAS population consists of all subjects who were assigned to a treatment arm and received at least one dose of study treatment.

A supportive analysis using the modified Full Analysis Set (mFAS) population will be performed for the primary (SVR_{12}) and key secondary efficacy endpoint (SVR_{24}). The mFAS population is a subset of the FAS, with subjects excluded for study discontinuation (lost to follow-up) with reasons unrelated to the treatment regimen. Examples of reasons for the exclusion of a subject include: failure to receive at least one dose of study treatment; loss to follow-up; missing data due to death with reasons unrelated to the study drug; discontinuation due to non-drug related AEs; informed consent and withdrawal.

Resistance Analysis (RA) Population will be used for resistance-associated variants (RAVs) analysis. The RA population is a subset of FAS, who either achieved SVR_{12} or met criteria for virologic failure (see Section 4). The RA does not include any subject who discontinued the study for reasons other than virologic failure. Baseline RAV analyses will be conducted in subjects for whom baseline sequencing data was available. Post-baseline RAV analyses will be limited to subjects who had both baseline and post-failure sequence data.

Details on the approach to handling missing data are provided in Section 8.6.1.

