- Treatment-Related Discontinuation = Failure (TRD=F) approach: The treatment related type 2 missing will be considered as failure; whereas the subjects who have the type 3 missing value and do not have virologic failure during the observed study period will be excluded from the analysis for the time points following their study withdrawal. Note that subjects with documented virologic failure during the treatment or follow-up period, even if they withdrew prematurely due to reasons not related to study drug, are classified as failures.
- Missing=Failure (M=F) approach: Any non-intermittent missing (i.e., type 2 and 3 missing) will be imputed as failure, regardless of the reason for study discontinuation.

In addition, a missing baseline/Day 1 HCV RNA result will be replaced with a screening result throughout all analyses, if available.

Proportion of Subjects With Virologic Responses

For the primary efficacy analysis based on the FAS population to estimate the proportions of subjects achieving SVR₁₂, 95% confidence intervals for these rates will be calculated using the Clopper-Pearson method [32] within treatment arms with no stratification. The missing data approach of M=F described above will be utilized for the primary analysis. The same method will be used to analyze all binary endpoints based on the FAS population.

The SVR₁₂ rates and confidence intervals for the randomized treatment-naïve F0-F2 subjects who received either 8 weeks of treatment or 12 weeks of treatment will be interpreted in the context of the historical clinical experience with EBR/GZR.

Sensitivity analyses will be performed for the primary endpoint and key secondary endpoint using the mFAS population with the TRD=F missing data approach. Under the assumption of missing completely at random (MCAR), the mFAS population excludes subjects who did not experience virologic failure, but prematurely withdraw from study due to reasons not related to the study drug (i.e., the subjects with the type 3 missing value). Note that subjects with documented virologic failure during the treatment or follow-up period, even if they withdrew prematurely due to reasons not related to study drug, are included in the mFAS population and classified as failures.

[Table 14](#) summarizes the key efficacy analyses and [Table 15](#) includes additional information on criteria to assess the primary endpoint (SVR₁₂) and key secondary endpoint (SVR₂₄).

Table 14 Analysis Strategy for Efficacy Variables

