Endpoint/Variable (Description, Time Point)	Primary vs. Supportive Approach	Statistical Method	Analysis Population	Missing Data Approach
Primary				
Proportion of subjects achieving SVR ₁₂ in each treatment arm	P	95% CI (Clopper-Pearson)	FAS	M=F
Proportion of subjects achieving SVR ₁₂ in each treatment arm	S	95% CI (Clopper-Pearson)	mFAS	TRD=F
Secondary				
Proportion of subjects achieving SVR ₂₄ in each treatment arm	P	95% CI (Clopper-Pearson)	FAS	M=F
Proportion of subjects achieving SVR ₂₄ in each treatment arm	S	95% CI (Clopper-Pearson)	mFAS	TRD=F
CI = confidence interval; M=F = Missing=Failure; P = Primary approach; S = Secondary approach; TRD=F = Treatment-Related Discontinuation=Failure.				

Table 15 Analysis Populations, Criteria for Response, Non-Response, and Exclusion from Analysis Population

Analysis Population	Criteria for Response	Criteria for Non-Response	Criteria for Exclusion From Analysis Population
FAS	HCV RNA < LLOQ	HCV RNA \geq LLOQ	Subject did not receive at least one dose of study medication
mFAS	HCV RNA < LLOQ for baseline infection [†]	HCV RNA \geq LLOQ for baseline infection	Subject discontinued from the study for non-treatment related reasons. Examples include: Loss to follow-up; d/c due non-drug related AEs; informed consent withdrawal.

FAS = full analysis set; HCV = hepatitis C virus; LLOQ = lower limit of quantification; mFAS = modified full analysis set; RNA = ribonucleic acid.

[†] This includes the case where HCV RNA \geq LLOQ but is demonstrated to be due to reinfection (after clearance of baseline infection)

Subject Virologic Failure: Non-response, Rebound, Virologic Breakthrough and Relapse

Summary statistics will be provided to describe the rates of occurrence of subject non-response, rebound, virologic breakthrough, and relapse. Definitions for subject virologic non-response, rebound, breakthrough, and relapse are in Section 4.2.3.1.1.2.

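### The relapse definition does not exclude reinfection, so a subject counted as an mFAS responder under Table 15 can also be counted as a relapse and as a source of emergent resistance

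*Combined protocol and SAP*

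**What the plan says.** **Relapse.** Section 4.2.3.1.1.2 requires confirmed HCV RNA at or above LLOQ "following end of all study therapy, after becoming undetectable (TND) at end of treatment". Section 7.1.5.5 restates this for "Subjects who meet the virologic failure criterion for relapse". Neither mentions reinfection.

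**Relapse rate.** The virologic failure summary in 8.6.1 refers back to 4.2.3.1.1.2 for its definitions.

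**Resistance.** The RA population in 8.5.1 comprises FAS subjects who achieved SVR12 or "met criteria for virologic failure (see Section 4"). The post-baseline RAV analysis needs baseline and post-failure sequences, but not evidence that they are the same strain. Section 4.2.3.1.2 says that "genotypic and investigational assays may be employed to differentiate virologic failure from re-infection". It requires no such assay and attaches no consequence to the result.

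**mFAS.** In Table 15, response is "HCV RNA < LLOQ for baseline infection". The footnote extends this to quantifiable virus that "is demonstrated to be due to reinfection (after clearance of baseline infection"). The 8.6.1 text says that subjects with documented virologic failure on treatment or in follow-up, "even if they withdrew prematurely due to reasons not related to study drug, are included in the mFAS population and classified as failures". That sentence has no reinfection exception.

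**FAS.** Table 15 treats any HCV RNA at or above LLOQ as non-response.

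**The concern.** The plan recognises in two places (Table 15 and 4.2.3.1.2) that reinfection after clearance is not a failure of treatment. It does not carry this into the definition that drives the relapse rate and the RA failures. A reinfected subject who was TND at end of treatment satisfies the relapse wording in full.

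Two outputs are exposed. Relapse is the failure type that bears most directly on whether 8 weeks is too short, the question raised in 4.2.1.2. Emergent RAVs in subjects who fail to achieve SVR are part of secondary objective 3. If a different virus is compared with the subject's own baseline sequence, strain differences can be reported as resistance emerging under EBR/GZR.

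**Working it through.** **1. One subject under each rule.** Take a subject who is TND at end of treatment and has confirmed quantifiable HCV RNA at FU12, above 1000 IU/mL. Sequencing shows a virus different from the baseline one.

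| Analysis | Governing text | Classification |
|---|---|---|
| FAS SVR12 and SVR24 | Table 15, FAS row | Non-response |
| mFAS SVR12 and SVR24 | Table 15 footnote | Response |
| mFAS, documented-failure sentence read literally | 8.6.1 text | Failure |
| Relapse rate | 8.6.1, by reference to 4.2.3.1.1.2 | Relapse |
| RA population | 8.5.1 | Virologic failure |
| Post-baseline RAVs | 8.5.1, paired sequences | Differences can be read as emergent |

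The second row conflicts with the last three. The third row is a possible reading only (see the objection).

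**2. Timing.** Reinfection by FU12 affects mFAS SVR12. Later reinfection affects only mFAS SVR24. A subject reinfected after SVR12 is in the RA population anyway as an SVR12 achiever, but still meets the relapse wording.

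**3. Inputs.** Expected arm sizes are 50 and 70 (8.9.1). The interval is two-sided 95% Clopper-Pearson (8.1, 8.6.1): lower limit = Beta quantile(0.025; x, n−x+1), upper limit = Beta quantile(0.975; x+1, n−x).

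**4. The plan's own figures.** All 13 intervals in Table 17 reproduce within rounding, for example 48/50 = 96.0% (86.3, 99.5) and 68/70 = 97.1% (90.1, 99.7). No stated figure is in dispute.

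**5. Shift per reinfected subject.** Arm 1: 1/50 = 2.0 points. Arm 2: 1/70 = 1.4 points. This takes the whole arm as the denominator; 8.6.1 does not state one for relapse.

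**6. Illustration.** Assume 2 true relapses per arm, k demonstrated reinfections by FU12, no other failures and nobody excluded from mFAS. The 2 is a placeholder; the shift per subject does not depend on it.

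| Arm | k | Relapse, definition as written | Relapse, reinfection excluded | mFAS SVR12, Table 15 | mFAS SVR12, 8.6.1 sentence read literally |
|---|---|---|---|---|---|
| 1 (n=50) | 1 | 3/50 = 6.0% (1.3, 16.5) | 2/50 = 4.0% (0.5, 13.7) | 48/50 = 96.0% (86.3, 99.5) | 47/50 = 94.0% (83.5, 98.7) |
| 1 (n=50) | 2 | 4/50 = 8.0% (2.2, 19.2) | 2/50 = 4.0% (0.5, 13.7) | 48/50 = 96.0% (86.3, 99.5) | 46/50 = 92.0% (80.8, 97.8) |
| 2 (n=70) | 1 | 3/70 = 4.3% (0.9, 12.0) | 2/70 = 2.9% (0.3, 9.9) | 68/70 = 97.1% (90.1, 99.7) | 67/70 = 95.7% (88.0, 99.1) |
| 2 (n=70) | 2 | 4/70 = 5.7% (1.6, 14.0) | 2/70 = 2.9% (0.3, 9.9) | 68/70 = 97.1% (90.1, 99.7) | 66/70 = 94.3% (86.0, 98.4) |

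With k = 0 the paired columns agree.

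**The case against.** The best defence is that the plan already separates the two concepts. Section 4.2.3.1.2 contrasts reinfection with virologic failure, and 8.5.1 points to Section 4 as a whole, so a demonstrated reinfection is arguably not a virologic failure at all. Entry to the RAV data also needs virus above 1000 IU/mL and paired sequences.

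This shows the intent but supplies no rule. The relapse summary refers to 4.2.3.1.1.2, where the definition has no exception, and not to the resistance section. Nothing says that a subject shown to be reinfected leaves the relapse count or the RA failures.

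The defence does succeed against two stronger inferences:

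- **A flat contradiction within mFAS.** A reader might infer this from the words "are included in the mFAS population and classified as failures". But that sentence follows the exclusion for missing data unrelated to study drug, and mainly stops known failures from leaving mFAS because they withdrew. Section 8.6.1 then refers to Table 15 for the endpoint criteria, and Table 15 addresses reinfection by name. The two can be read consistently; the sentence merely lacks the exception.
- **Failures moved to response at will.** A reader might infer this from optional testing in an open-label trial. But Table 15 requires reinfection to be demonstrated, so an untested or inconclusive case stays an mFAS non-response. Failure samples above 1000 IU/mL are to be tested for resistance in any case (4.2.3.1.2, 8.6.3). Only the step of comparing strains is discretionary.

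**Conclusion.** The point holds as an error in the relapse rule with limited reach. Followed as written, the definition counts a subject with demonstrated reinfection as a relapse and admits the subject to the RA population as a failure, while Table 15 counts the same subject as an mFAS responder. That the new virus would be reported as emergent RAVs is possible, not certain.

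The size is 2.0 points on the relapse rate per subject in Arm 1 and 1.4 in Arm 2. The mFAS SVR rate shifts by the same amount only if the documented-failure sentence is read literally. The number of reinfections is an assumption (0 to 2 per arm).

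A reader might go further and infer that reinfection would make up a large share of the failures. The documents do not support this, because they give no expected number of relapses. The n=50 scenarios in Table 17 run from 45 to 49 responders, that is 50−45 = 5 down to 50−49 = 1 non-responders of any kind.

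The primary FAS analysis has one consistent rule and does not move. The effect is confined to the descriptive relapse rate, the emergent-RAV description and, on the literal reading, the supportive mFAS analysis. This is a modest wording correction.

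**What to change.** 1. In 4.2.3.1.1.2, and by reference in 7.1.5.5, state that viraemia demonstrated to be reinfection is not relapse.
2. Cross-refer from 8.5.1 and 8.6.1: list demonstrated reinfections separately, and exclude them from the relapse rate and from the RA failures. Add the same exception to the documented-failure sentence so that it plainly agrees with Table 15.
3. Replace the optional assay with a routine comparison of baseline and post-treatment sequences for every subject with confirmed post-treatment HCV RNA above 1000 IU/mL. Where the comparison is not possible (including virus between LLOQ and that threshold) or is inconclusive, count the subject as a relapse.
4. Leave the FAS rule as it is.

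The cost is wording and a small amount of extra analysis, because sequencing of baseline and failure samples is already planned. Section 8.0 allows changes to analyses before final database lock to be documented in a supplemental SAP; the definition in Section 4 is protocol text.

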8.6.2 Statistical Methods for Safety Analyses

Safety and tolerability will be assessed by clinical review of all relevant parameters including adverse experiences and laboratory parameters.

The proportion of subjects with adverse experiences of elevated laboratory values that are reported as ECIs described in Section 7.2.3.2 during the study therapy period are prespecified as events of clinical interest and will be provided.

In addition, the broad clinical and laboratory AE categories consisting of the percentage of subjects with any AE, a drug related AE, a serious AE, an AE which is both drug-related and serious, and who discontinued due to an AE will be summarized in the same manner (Table 16). Laboratory parameters will be summarized by pre-defined limits of change, laboratory grade shift summaries, and for selected laboratory parameters, change from baseline summaries.

In this estimation study, rates of events of clinical interest (as defined in Section 7.2.3.2) as well as broad categories of adverse events will be reported along with 95% confidence intervals for safety monitoring. Rates will also be shown for all specific AEs reported and pre-determined limits of change in laboratory results.

Missing safety parameter values will be handled using the Data-As-Observed (DAO) approach, that is, any missing value will be excluded from the analysis. For lab shift summaries, change from baseline summaries and certain pre-defined limits of change summaries require a baseline value. If a baseline value is missing, the latest pre-treatment value will be used instead. If no pre-treatment result is available, that subject will not be included in the summary. The safety summarization of results will be presented by treatment arm (Arm 1 and Arm 2) unless otherwise specified.

Table 16 Analysis Strategy for Safety Parameters

Safety Endpoint [†]	95% CI [‡]	Descriptive Statistics
AEs of elevated laboratory values that are reported as ECIs	X	X
Any AE	X	X
Any SAE	X	X
Any drug-related AE	X	X
Any serious and drug-related AE	X	X
Discontinuation due to AE	X	X
Specific AEs, SOCs, or PDLCs Change from baseline results (laboratory results, vital signs)		X X

AE = adverse event; CI = confidence interval; ECI = clinical event of interest; PDLC = pre-defined limit of change; SOC = system organ class; X = results will be provided.
† Adverse experience references refer to both clinical and laboratory AEs.
‡ 95% CIs are provided for selected endpoints in this estimation study for safety monitoring.

8.6.3 Summaries of Baseline Characteristics, Demographics, and Other Analyses

Demographic and Baseline Characteristics

No statistical hypothesis tests will be performed on these characteristics. The number and percentage of subjects screened, enrolled, the primary reasons for screen failure, and the primary reason for discontinuation will be displayed. Demographic variables (e.g., age, gender, and genotype subtype), primary and secondary diagnoses, and prior and concomitant therapies will be summarized using descriptive statistics for continuous or categorical variables, as appropriate. Summary statistics for the baseline efficacy measure (HCV RNA) will also be provided.

Viral Resistance Measurements

Viral resistance testing will focus on the entire NS3/4A and NS5A regions for all subjects and for those who meet the subject virologic failure criteria (see Section 4.2.3.1.1.2).

8.7 Interim Analysis

No interim analyses are planned for this study.

8.8 Multiplicity

There will be no multiplicity adjustments in the analyses of this study.

8.9 Sample Size and Power Calculation

An initial description of sample size is provided in Section 4.2.1.6.

The expected sample size for each treatment arm in this study (N=50, and 70) was selected based on the knowledge of the epidemiology of HCV infection in France. This is an exploratory study and the samples sizes are reflective of the number of patients that are likely to be enrolled in each treatment arm and are not driven by statistical consideration.

